### **Drug Abuse and Dependence**

There are currently no data on drug abuse or dependence with TS23; however, it is considered that no potential exists.

---

### 6.1.2 Dosing and Administration

In the SISTER trial, five different dose cohorts will be studied:

Cohort 1: placebo (for TS23)

Cohort 2: 3.0 mg/kg TS23

Cohort 3: 5.0 mg/kg TS23

Cohort 4: 7.0 mg/kg TS23

Cohort 5: 10.0 mg/kg TS23

The doses will be administered according to the following dosing provided in [Table 2](#).

**Table 2. Dosing Based on Patient Weight**

| Weight (kg) | TS23 dose mgs |         |         |          |
|-------------|---------------|---------|---------|----------|
|             | 3 mg/kg       | 5 mg/kg | 7 mg/kg | 10 mg/kg |
| <60         | 180           | 300     | 420     | 600      |
| 60 to <70   | 210           | 350     | 490     | 700      |
| 70 to <80   | 240           | 400     | 560     | 800      |
| 80 to <90   | 270           | 450     | 630     | 900      |
| ≥90         | 300           | 500     | 700     | 1000     |

TS23 study drug is provided in 10 ml vials at a concentration of 10 mg/ml. The study drug will be diluted by the study pharmacist with sterile 0.9% saline to a total volume of 200 ml for infusion as described in the Pharmacy Manual. A placebo solution consisting of 200 ml of the diluent (0.9% saline for infusion) will be dosed in a similar manner to maintain the double-blind study design. TS23 diluted for infusion with 0.9% saline and 0.9% saline have a similar appearance. The diluted study drug or placebo will be given to the study team by an unblinded site pharmacist without indication of the identity of the drug, so as to maintain blinding. Participants will either receive the study drug (200 ml) or 0.9% saline placebo (200 ml), which will be given intravenously as a single dose, over an infusion time of about ~15 minutes. At the highest dose of TS23, this corresponds to a maximum rate of  $\leq 0.67$  mg/kg/min.

## 6.2 Preparation/Handling/Storage/Accountability

### 6.2.1 Acquisition and accountability

The StrokeNet Central Pharmacy will distribute study drug to participating sites using the WebDCU™ system. Initial investigational product supply will automatically be supplied to each site following collection of regulatory documents, site training, and completion of the site readiness call. Automatic resupply will occur when the WebDCU™ system determines additional investigational product is required at the site.

When a drug shipment is received, the site or site pharmacists will check the amount and condition of the drug, check for appropriate local language in the label, drug expiration date, and acknowledge receipt in WebDCU, and contact StrokeNet pharmacy as soon as possible if there is a problem with the shipment. A Drug Accountability Record will be provided for the investigational study drug. The record must be kept current and should contain the dates and quantities of study drug received, the subject to whom the study drug was dispensed (via identification number and/or initials or supply number as applicable), the date and quantity of study drug dispensed and remaining, as well as the initials of the dispenser.

At the end of the study, or as directed, all investigational product supplied by the Sponsor, with all discrepancy resolved, including unused, partially used, or empty containers, will be destroyed at the site according to the site's drug handling and disposition SOPs or returned to Strokenet Central Pharmacy if required by site institutional policy. A copy of these SOPs must be available onsite. The certificate of destruction must be provided to Translational Sciences that documents the drug, the quantity (vials), method of destruction, and date of destruction.

The Investigational Product will be destroyed or returned only after the study monitor or alternatively the site, according to their instructional SOPs, has completed a final inventory to verify the quantity to be destroyed or returned. The destruction of study drug must be documented, and the documentation filed and in case of returns included in the shipment. At the end of the study, a final study drug reconciliation statement must be completed by the Investigator or designee and provided to the Sponsor. All Investigational Product inventory forms must be made available for inspection by a Sponsor authorized representative or designee and regulatory agency inspectors. The Investigator is responsible for the accountability of all used and unused study supplies at the site.

### **6.2.2 Formulation, Appearance, Packaging, and Labeling**

The investigational product TS23 is manufactured under the direction of Translational Sciences, Inc. by Cytovance Biologics, Inc. TS23 is supplied in 10 ml stoppered vials that will be labeled as an investigational drug with appropriate study identifiers to permit tracking of vials. Each vial contains 10 mL of a 10 mg/mL solution of TS23 in a phosphate buffer-based formulation (10 mM sodium phosphate, 50 mM sodium chloride, 5% Sorbitol, pH 6.0). It appears as a clear liquid, virtually free of particles.

Details of the packaging and labeling of TS23 10 mL of 10 mg/mL solution for infusion and matching placebo will be provided in the pharmacy instructions.

Packaging and labeling will be performed according to GMP.

### **6.2.3 Product Storage and Stability**

TS23 drug supplies must be stored in a secure, limited access storage area at 2-8°C (36-46°F) and protected from light. In the event of an excursion from storage requirements, the site will quarantine the investigational product and consult the Sponsor to determine whether the investigational product can be used.

---

#### **6.2.4 Preparation**

The doses for administration of TS23 are weight-based. To preserve blinding, TS23 and its placebo will be administered as the same volumes and rates of IV infusion.

TS23 is available in single-use vials containing 10 mL of 10 mg/mL of product for IV infusion. This will be diluted in 0.9% saline approved for IV injection to a total volume 200 ml per subject. It will be infused over 15 min. as described in the Pharmacy Manual

The placebo will be sterile, 0.9% saline alone in a volume of 200 ml. It will also be infused over 15 min. as described in the Pharmacy Manual

### **6.3 Measures to Minimize Bias: Randomization and Blinding**

#### **6.3.1 Randomization**

A web-based central randomization system will be developed by the National Data Management Center (NDMC) and available for use via WebDCU™. The objective of randomization is to prevent possible selection bias by providing random treatment assignment to each subject, and to prevent accidental treatment imbalances for the known prognostic variables. Balancing of prognostic variables will be conducted using the Minimal Sufficient Balance randomization algorithm which aims to maximize the treatment allocation randomness while containing the baseline covariate imbalances. The randomization will not be stratified by study site. With a total of 50 active sites enrolling at a given time during the study, who are enrolling at an average rate of 2.5 patients/year, it will be nearly impossible for local investigators to be able to inadvertently guess the randomization order.

Randomization will occur via the study-specific password-protected website accessed by an authorized research coordinator or investigator at the clinical site. If, in rare circumstances, the web system is not available, the coordinator or investigator will have access to a 24/7 emergency randomization hotline that will allow the site to randomize the subject. Upon randomization by the authorized person at each center, an e-mail notification will be sent to the Site Principal Investigator (PI), Site Primary Study Coordinator and relevant StrokeNet National Clinical Coordinating Center (NCC) and NDMC personnel.

#### **6.3.2 Blinding**

SISTER will employ a prospective, randomized, double-blinded, placebo-control trial design. Participants and local investigators will be blinded to the study group assignment. Only the local pharmacist will be aware of this group assignment; the local pharmacist will not have direct subject contact and will have no participation in outcome adjudication.

All clinical (including laboratory) and imaging outcome assessments will be performed by trained personnel who will be blinded to participants' study group assignment at 3(+/-1) hour, 30 (+/-4) hour, 30 (±5) days, and 90 (±7) days. NIHSS will be assessed by certified raters. The mRS will be rated by raters certified in the Rankin Focused Assessment (RFA) method. (Saver, Filip et al. 2010, Banzon,

---

Patel et al. 2013, Patel, Starkman et al. 2016) All imaging outcomes will be centrally adjudicated by trained readers who are blinded to the participant's study group assignment.

#### **6.4 Study Intervention Compliance**

The TS23 is given by short-lived administrations (15 mins). Thus, study intervention compliance will be monitored closely by direct observation of study drug administration by the local study staff. If the study drug is discontinued after initiation, the reason for discontinuation, total duration of administration and total dose administered will be noted in the Case Report Form (CRF) by the local study personnel.

#### **6.5 Concomitant Therapy**

For this protocol, a prescription medication is defined as a medication that can be prescribed only by a properly authorized/licensed clinician. Medications to be reported in the CRF are concomitant prescription medications, over-the-counter medications, and supplements.

##### **6.5.1 Rescue Medicine**

In case of symptomatic ICH or major systemic bleeding event, antifibrinolytic agents such as epsilon amino caproic acid (Amicar) or tranexamic acid (Lysteda) should be considered and used according to the package insert.

### **7 STUDY INTERVENTION DISCONTINUATION AND PARTICIPANT DISCONTINUATION/WITHDRAWAL**

#### **7.1 Discontinuation of Study Intervention**

All patients enrolled in the SISTER trial will be monitored during the study drug administration and for at least 4 hours following the completing of drug administration in high acuity setting (such as the emergency department, intermediate care unit or ICU) for development of adverse reactions and without disruption of the standard clinical care. No dose reductions are allowed in this study. Temporary interruptions in the administration of study drug infusions, other than brief ones to address a blocked IV line, are also not allowed in this study. It is expected that all randomized participants will receive the complete treatment (~15 minutes infusion), unless there is a safety issue that prevents completion of the infusion. If the patient develops hemorrhagic complications or anaphylaxis to the drug administration, the study medication may be halted. In such an event, the patient will be treated for the complications per the local investigators' best judgement.

If there is a need to interrupt administration of the study drug infusion because of a safety concern, then study drug administration must be permanently discontinued. The reason for discontinuation and the amount of dose administered will be documented.

Information regarding the type of reaction leading to discontinuation of study intervention, total duration of administration, total dose administered, and treatment needed for the reaction will be noted

---

on the CRF. The event responsible for study drug discontinuation will be noted as an AE or SAE and/or UP (Please see Section 9 below).

Discontinuation from study intervention does not mean discontinuation from the study, and remaining study procedures should be completed as indicated by the study protocol. If a clinically significant finding is identified (including, but not limited to changes from baseline) after enrollment, the investigator or qualified designee will determine if any change in participant management is needed. Any new clinically relevant finding will be reported as an AE.

## 7.2 Participant Discontinuation/Withdrawal from the Study

Participants are free to withdraw from participation in the study at any time upon request.

The reason for participant withdrawal from the study will be recorded on the CRF. Participants who sign the informed consent form and are randomized but do not receive the study intervention may be replaced. Participants who sign the informed consent form, and are randomized and receive the study intervention, and subsequently withdraw, or are withdrawn from the study, will not be replaced.

## 7.3 Lost to Follow-Up

When scheduling follow-up visits, multiple attempts should be made in order to reach the participant. If the participant cannot be reached, multiple attempts should be made to the person(s) listed as secondary contact. If no contact is made after multiple attempts, alternative methods should be considered in order to obtain contact with the participant and/or verify their living status. Examples of alternative methods of contact are fax, other scheduled medical appointments, and certified letter.

**Efforts should be made for up to 150 days from randomization to determine the participants' 90-day status.** A participant may be considered lost to follow-up if they cannot be reached for up to 150 days from randomization, despite following the procedures outlined above. The following are considered to be reasons a subject is lost to follow-up: unable to contact for follow-up, moved away from and unable to return for follow-up visits. Appropriate documentation of lost to follow-up will be maintained in the subject's research record at the site.

All effort is put forth to ensure complete follow-up for all participants that had study drug initiated, in particular with the assessment of the primary outcome at 24-30 hr. This is expected to be extremely rare for patients enrolled in SISTER given that majority of the patients will be admitted to the hospital at least for the duration of 24-30 hours following their acute stroke. The study personnel will note the patient's name, date-of birth, and medical record numbers upon enrollment. They will also clearly communicate and remind the clinical care teams about the study assessment timeline to from time-to-time. Other measures taken to minimize loss to follow-up will be outlined in site-specific SOPs. It is possible that a small fraction of patients may die before completing the 30 ( $\pm 4$ ) hour assessments. Our plan to account for such missing data is outlined in the statistical analysis plan (SAP).

## 8 STUDY VISITS

The following core data will be abstracted for all patients enrolled in the SISTER trial.

---

## 8.1 Baseline

Patients presenting with acute ischemic stroke will be evaluated by a stroke team physician, in accordance with institutional practice, to establish study eligibility. All consecutive patients meeting study entry criteria will be enrolled in the trial.

Participants enrolled in SISTER should not receive antithrombotics for at least 24 hours after study drug administration.

The study order sets will specifically include an order not to administer antithrombotics within the first 24 hours after study drug administration. This will also be closely monitored as participants will be admitted to the intensive care unit setting for at least first 24 hours after drug admission.

The following data will be documented at the baseline evaluation for randomized patients:

- Demographics: Age, sex, race/ethnicity
  - Medical history regarding presence of concomitant medical conditions (e.g. hypertension, diabetes, hyperlipidemia, atrial fibrillation, prior ischemic stroke, prior hemorrhagic stroke, current or past smoking)
  - Vital signs: Systolic and diastolic arterial blood pressure; heart rate, temperature
  - Concomitant medications at time of stroke onset (anticoagulation, antiplatelets, antihypertensives, statins, antidiabetics, cholesterol reducers)
  - Pre-stroke functional state: pre-stroke modified Rankin Scale, pre-stroke ambulatory status (independent, with assistance, unable)
  - Laboratory Evaluation
    - Measurement within 12 hours prior to study drug administration (if there are multiple measurements, then consider the latest measurement)
      - SOC: aPTT, PT with INR, CBC, platelet count.
    - First measurements upon presentation to study hospital, within 2-3 hours of study drug administration):
      - SOC: Glucose, creatinine
    - First value collected during hospitalization:
      - SOC: Hemoglobin A1C, Lipid Panel containing total cholesterol, HDL, LDL & triglyceride.
  - Neurologic Deficit: NIHSS upon arrival to the study hospital
-

- Brain and Vascular imaging at presentation:
    - CT or MRI
    - CTA or MR angiography (MRA)
    - CTP or MRI-PWI, if applicable per institutional practices
  - Initial Workflow Time Metrics: Date and time of:
    - Last known well (LKW)
    - Symptoms first observed (SFO)
    - Outside hospital (OSH) date/times (if patient first presented to an OSH):
      - Arrival at OSH (“Door-In”)
      - Departure from OSH (“Door-Out”)
    - Study Hospital date/times:
      - Arrival at Study Hospital
      - Initial brain parenchymal imaging (NCCT or DWI MRI)
      - Initial vascular or perfusion imaging (CTA or MRA; CTP or PWI-MR)
  - Findings on First Imaging at Presentation (per site)
    - NCCT or MRI
      - ASPECTS
      - Any Radiologic Hemorrhage
    - CTA or MRA
      - Presence of a visible vessel occlusion
      - Location of vessel occlusion if present (per the central reader): ICA, M1 MCA, M2 MCA, M3/M4 MCA, A1 ACA, A2-5 ACA, VA, BA, P1 PCA, P2 PCA, P3/4 PCA, PICA, AICA, SCA, Other
  - CTP or Perfusion/Diffusion MR (PWI MR)
-

- Perfusion lesion volume (volumes of regions with  $T_{\max} > 6$  sec and  $>10$  sec on CTP or PWI MR)
- Ischemic core lesion volume (on CTP -volume of region with  $rCBF < 30\%$ ; on DWI-volume of region with  $ADC < 620 \times 10^{-3}$  mm/s)

## 8.2 Pre-Randomization/Randomization visit

- Time of randomization
- Time of study drug administration
- Time of study drug completion
- Baseline research related laboratory studies (prior to study drug administration):
  - Fibrinogen – processed and resulted at site.
  - a2AP, MMP-9 levels and PK studies – processed and frozen. This will be shipped to the central laboratory

## 8.3 3 ( $\pm 1$ ) Hours Post Study Drug Administration

- Research labs:
  - Fibrinogen - processed and resulted at site.
  - a2AP, and MMP-9 levels and PK studies - processed and frozen. This will be shipped to the central laboratory

## 8.4 30 ( $\pm 4$ ) Hours Post Study Drug Administration

- Research related labs:
    - Fibrinogen, PT/INR, aPTT to be processed and resulted at site
    - a2AP, and MMP-9 levels and PK studies to be processed and frozen. This will be shipped to the central laboratory
  - SOC Labs:
    - CBC
-

- NIHSS assessed by blinded, certified rater
  - Basic metabolic panel (glucose, calcium, sodium, potassium, carbon dioxide, and chloride, BUN creatinine) at 30 ( $\pm 4$ ) hours post study drug administration if done as standard of care
  - Vital Signs
  - Non contrast CT Brain (reading will be performed centrally) (**Please note that an MRI cannot substitute for the CT**)
    - ASPECTS score
    - Any radiologic hemorrhage (further classified as SAH, HI1, HI2, PH1, PH2, RIH, IVH, SDH, EDH) on CT
  - CTA or MRA head (required only if visible vessel occlusion present on the baseline CTA or MRA per site read).
    - Presence of a visible vessel occlusion
    - Location of vessel occlusion (per the central reader): ICA, M1 MCA, M2 MCA, M3/M4 MCA, A1 ACA, A2-5 ACA, VA, BA, P1 PCA, P2 PCA, P3/4 PCA, PICA, AICA, SCA, Other
  - CT/MR perfusion
    - Perfusion lesion volume (volumes of regions with  $T_{\max} > 6$  sec and  $> 10$  sec on CTP or PWI MR)
    - Ischemic core lesion volume (on CTP -volume of region with  $rCBF < 30\%$ ; on DWI-volume of region with  $ADC < 620 \times 10^{-3}$  mm/s)
    - If the participant underwent CT perfusion at baseline, then CT perfusion should be obtained at 30 ( $\pm 4$ ) hours.
    - If the participant underwent MR perfusion at baseline, then MR perfusion should be obtained at 30 ( $\pm 4$ ) hours.
  - Symptomatic intracranial hemorrhage [symptomatic ICH, as per SITS-MOST definition (a local or remote type II parenchymal hemorrhage within 30 ( $\pm 4$ ) h after treatment associated with a  $\geq 4$ -point deterioration on the NIHSS score from baseline or from the lowest score from baseline to 24 hours, or leading to death.)] ([Wahlgren, Ahmed et al. 2007](#))
  - Major non-ICH systemic hemorrhage
  - Clinically relevant systemic hemorrhage
-

- AE
- SAE
- UPs

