## 1.2 Schema

### 1.3 Schedule of Activities (SoA)

| Schedule of Activities    |                                  |                           |  |                                   |                                       |                 |                |                |
|---------------------------|----------------------------------|---------------------------|--|-----------------------------------|---------------------------------------|-----------------|----------------|----------------|
|                           |                                  |                           | Time after initiation of study drug administration |                                   |                                       |                 |                |                |
|                           | Baseline                         | Study drug administration | 3 (±1) hours                                       | 30 (±4) hours**                   | 72 (±12)/ Discharge, whichever is 1st | Discharge Visit | Day 30±5       | Day 90±7       |
| Screening & Eligibility   | X R                   |                           |  |                                   |                                       |                 |                |                |
| Medical History           | X S                   |                           |  |                                   |                                       |                 |                |                |
| Laboratory Studies        | X S & X R  | X R*           | X R*                                    | X S & X R** |                                       |                 |                | X R |
| Pre-stroke mRS            | X R                   |                           |  |                                   |                                       |                 |                |                |
| NIH stroke scale          | X R                   |                           |  | X R                    | X R                        |                 | X R | X R |
| Vital Signs               | X S                   |                           |  | X S                    |                                       |                 |                |                |

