## **6 STUDY INTERVENTION**

### **6.1 Study Intervention(s) Administration**

#### **6.1.1 Study Intervention Description**

TS23 is an IgG2 chimeric antibody that inactivates human a2AP. TS23 is expected to enhance the dissolution of thrombi by removing the inhibitory effects of a2AP on the fibrinolytic process.

Participants enrolled in SISTER should not receive antithrombotics for at least 24 hours after study drug administration.

The study order sets will specifically include an order not to administer antithrombotics within the first 24 hours after study drug administration. This will also be closely monitored as participants will be admitted to the intensive care unit setting for at least first 24 hours after drug admission.

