### 9.2 Secondary safety endpoints

1. Incidence of symptomatic ICH within 30 ( $\pm 4$ ) h of study drug administration (SITS-MOST definition). ([Wahlgren, Ahmed et al. 2007](#)) The presence of type-2 parenchymal hematoma will be determined by a central, blinded, neuroradiologist and a worsening in NIHSS will be determined by the NIHSS reported on the study CRF by the local, certified, blinded assessors.
2. Incidence of non-ICH major or clinically relevant non-major bleeding within 30 days of study drug administration.

Non-ICH major bleeding is defined as clinically overt bleeding, that is not ICH, with one or more of the following:

- causing a fall in hemoglobin of 2 g/dL or more,
  - or leading to a transfusion of 2 or more units of packed red blood cells or whole blood,
-

- symptomatic and occurring in a critical site: intracranial, intraspinal, intraocular, pericardial, intra- articular, intramuscular with compartment syndrome, retroperitoneal,
- contributing to death.

Clinically relevant non-major (CRNM) bleeding is defined as overt bleeding not meeting the criteria for major bleeding that requires medical attention or is associated with discomfort for the subject such as pain, or impairment of activities of daily life.

All other overt bleeding episodes not meeting the criteria for major or CRNM bleeding will be classified as nuisance bleeding.

Symptomatic ICH, non-ICH major bleeding, and CRNM will be adjudicated by the study independent medical monitor (IMM)

3. Non-bleeding, SAEs within 90 ( $\pm 7$ ) days will be determined by direct interview during all study visits.
4. Incidence of stroke-related and all-cause deaths within 90 ( $\pm 7$ ) days will be determined by direct interview.
5. Plasma fibrinogen levels at 3 (+/-1) h after completion of TS23 therapy will be determined by laboratory testing of study-specific blood draw.

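### The symptomatic ICH definition relies on the lowest NIHSS in the first 24 hours, but the protocol schedules no NIHSS between baseline and the 30 (±4) h visit

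*Protocol*

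**What the plan says.** Symptomatic ICH is the first secondary safety endpoint (protocol sections 1.1, 3.2 and 9.2) and an adverse event of special interest (section 9.3.7). Sections 1.1 and 8.4 spell out the SITS-MOST definition: a local or remote type II parenchymal hemorrhage within the 30 h window, with at least a 4-point "deterioration on the NIHSS score from baseline or from the lowest score from baseline to 24 hours, or leading to death".

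Section 9.2 names the data source: "a worsening in NIHSS will be determined by the NIHSS reported on the study CRF by the local, certified, blinded assessors".

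The scores available are these:

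- Baseline, section 8.1: "Neurologic Deficit: NIHSS upon arrival to the study hospital". This is a single score.
- The "NIH stroke scale" row in section 1.3 is marked at baseline, 30 (±4) h, 72 (±12) h or discharge, day 30 and day 90. The cells for study drug administration and 3 (±1) h are empty.
- Section 8.3 lists only research laboratory work at 3 (±1) h, beginning with "Fibrinogen - processed and resulted at site".
- Section 8.4 has the first score after dosing: "NIHSS assessed by blinded, certified rater".

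**The concern.** The definition has two NIHSS reference points, baseline and the lowest score up to 24 h. The second exists to catch patients who improve and then deteriorate because of a bleed. It needs at least one score after dosing and before 24 h, and the protocol requires none. A statistical analysis plan cannot repair this, because it cannot recover scores that were never recorded.

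What is at stake is the count of symptomatic ICH and whether it can be compared across arms. The patients at risk of being left out are those who improved early. If TS23 works early, there would be more of them on active doses than on placebo, and the error would make active doses look safer on this endpoint. There is also a risk of inconsistent counts: a site could report an adverse event of special interest from bedside scores while the endpoint derived from CRF scores says no event occurred.

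**Working it through.** The protocol gives no rate, power or sample size for symptomatic ICH, so there is no figure to reproduce. The check compares the schedule with the definition.

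**Step 1: scores inside the window.** The earliest scheduled score after dosing is at 30 − 4 = 26 h (sections 1.3 and 8.4). The window for the lowest score closes at 24 h. The score at 72 h or discharge is not expected to fall inside it, since participants are to be "admitted to the intensive care unit setting for at least first 24 hours after drug admission" (section 6.1.1). Scheduled scores after dosing and up to 24 h: zero.

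**Step 2: effect on the rule.** Let B be the baseline score, k the true early improvement (so the true lowest score is B − k), and X the score at 30 h.

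- By the definition, a non-fatal type II hematoma counts if X − (B − k) ≥ 4, that is X ≥ B − k + 4.
- On scheduled data the lowest score equals B, so it counts only if X ≥ B + 4.
- Cases with B − k + 4 ≤ X ≤ B + 3 are symptomatic ICH by the definition but are not counted.

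The worsening needed from the true lowest score is therefore 4 + k: 6 points for k = 2, 8 for k = 4 and 12 for k = 8.

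**Step 3: an example with assumed scores.** Baseline 16, 6 at 3 h, type II hematoma, 13 at 30 h.

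- From baseline: 13 − 16 = −3, not counted.
- From the true lowest score: 13 − 6 = +7, counted by the definition.

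**Step 4: what is still counted.** Type II hematomas leading to death count regardless of NIHSS. So do those with a 30 h score at least 4 above baseline. Any hemorrhage on the 30 h CT counts in the primary safety endpoint (section 9.1) and is classified by type (section 8.4).

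**Step 5: scale, on assumptions.** At full enrollment, placebo has 10 + 5 × 13 = 75 participants (section 4.1). The four doses share 300 − 75 = 225, an average of 225 / 4 ≈ 56, with adaptive allocation. Suppose symptomatic ICH occurs in 3–6%, which is the r-tPA figure in section 2.5.1 and not an estimate for TS23. Expected events are then 75 × 0.03 = 2.3 to 75 × 0.06 = 4.5 on placebo, and 56 × 0.03 = 1.7 to 56 × 0.06 = 3.4 on an average active dose. Counts this small are sensitive to a single reclassified case, but nothing in the protocol gives the probability that a case is missed.

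**The case against.** The strongest reply has four parts.

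- *Little escapes safety review.* Any ICH on the 30 h CT is read centrally and blinded. The safety utility (section 10.2.2) and the safety posterior (section 10.2.3.2) use any ICH, not symptomatic ICH. A deterioration at any time is recorded as an adverse event (section 9.3.4), and the independent medical monitor adjudicates symptomatic ICH and reviews SAEs (sections 9.2 and 9.5). All of this stands. It confines the problem to the secondary endpoint and the adverse event of special interest.
- *The CRF may hold unscheduled scores.* Section 9.2 does not restrict the source to scheduled visits, and the CRF and manual of procedures are not shown. This stands as a limit: the supportable claim is that the protocol does not require an early score. Equally, nothing in it asks for serial or event-triggered scores, or lets the monitor substitute chart scores for CRF scores.
- *Section 6.3.2 mentions blinded clinical assessments at 3 (±1) h.* That sentence includes laboratory assessments, and sections 1.3 and 8.3 place no NIHSS at that time. This part does not stand.
- *The example is extreme.* It assumes a 10-point improvement by 3 h, whereas full efficacy utility corresponds to a 2-point mean difference from control. It shows how the rule behaves, not how often the case arises.

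Two stronger readings are tempting. A reader might infer that all bleeds after early improvement are missed. Step 4 shows otherwise. A reader might also infer that 20–50% of events would be lost, since one case out of two to five is that share. That presupposes a miss, uses a borrowed rate, and takes an arm of 75, which matches placebo and not the active doses where the loss is feared.

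**Conclusion.** The definition and the schedule do not fit together. On scheduled data the lowest-score clause is inoperative, and the endpoint reduces to worsening from baseline to 30 h, or death. Non-fatal type II hematomas after early improvement, with a 30 h NIHSS less than 4 points above baseline, would not be counted as symptomatic ICH.

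The number of such cases cannot be estimated from the protocol. That the undercount would fall more on active arms is conditional on TS23 improving NIHSS before the bleed. A reader might go further and conclude that dose selection or the go decision is biased. The document does not support that, because the primary safety endpoint, the utility, the stopping rule and the success criterion do not use symptomatic ICH. This is a worthwhile, inexpensive correction to a named secondary safety endpoint, not a flaw in the primary analysis.

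**What to change.** In the schedule of activities and sections 8.3 and 8.4:

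- record NIHSS on the CRF at the existing 3 (±1) h contact;
- enter the lowest NIHSS documented in routine care up to 24 h;
- enter any NIHSS taken at neurological worsening or at an unscheduled brain CT up to the 30 h visit.

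State in section 9.2 that these scores are used for the lowest-score comparison. The routine-care and event-triggered entries matter, because a 3 h score alone recovers the lowest score only in part.

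The cost is a few minutes of site time per patient and a few CRF fields. No sample size changes. A lowest point falling between recorded scores may still be missed.

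If early scores will not be collected, restate the endpoint as worsening from baseline only, and do not describe it as the full SITS-MOST definition.
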